To accomplish the aims of assessing the impact of adjunctive US-guided DOT on reducing benign biopsy recommendation (i.e. FPs), while maintaining sensitivity (i.e. TPs) we will conduct a reader study of the 300 subject trial. Three of four study radiologists will serve as study readers for each case. (To eliminate potential bias a study radiologist performing the biopsy will not serve as a reader for that case.) As noted above the study radiologist who performs or supervises the US-guided DOT exam will be one of the readers. Two additional study radiologist readers will subsequently and independently review the available pre-existing patient information and CI data, (excluding the US-guided biopsy exam) and complete CI and DOT CRFs blinded to the pathology result of the abnormality that underwent biopsy. The CRFs include a BI-RADS assessment. The reader will first complete the CI CRF blinded to the US-guided DOT result, then after reviewing the optical data (tHB concentration and distribution) the reader will complete the DOT CRF including the impact of US-guided DOT information on the BI-RADS assessment, i.e. no change, decreased or increased.

Similar to the CI plus DOT workflow, for cases that have CEM, a CI CRF will be completed first, followed by a CEM specific CRF including a BI-RADS assessment and the impact of CEM on the BI-RADS assessment will be recorded. As noted above, the study radiologist that supervises the US-guided DOT and CEM exams will serve as one of the study readers. For the subsequent two readers we will alternate which adjunctive modality (i.e. CEM or US-DOT) is reviewed first and separate the subsequent review of the second adjunctive modality by a minimum of 4 weeks to prevent recollection bias).

Figure 4 diagrams the core analysis. Combined CI and US-guided DOT BI-RADS 2 and 3 assessments will be considered test negative, and BI-RADS 4A, 4B, 4C, and 5 assessments will be considered test positive. For negative tests, the biopsy proven malignant group (Gc, see Fig. 1(b)) represents false negative results, and the benign group Gd represents true negatives and reflects the potential reduction in benign biopsy recommendation if US-guided DOT were used as SOC. Ga represent true positives and Gb represent false positives utilizing adjunctive US-guided DOT. A comparison of the Ga groups i.e. CI alone vs. CI & DOT will constitute the assessment of the effect of adjunctive US-guided DOT on sensitivity.

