7.1 Data Analysis and Validation

US-guided DOT database and Training:

Part 1 - Using typical tHb levels and features (e.g. peripheral enhancement, shadowing) from biopsy proven benign and malignant cases obtained from earlier studies we will train the four study radiologists. The goals of the training are to familiarize the study radiologists with US-guided DOT imaging and typical hemoglobin distributions (tHb, oxyHb, deoxyHb) of different benign and malignant disease processes and to assess intra- and inter-observer variability. Data from the training study will not be used in the primary analysis.

Part 2 - Approximately 20 patients will be enrolled for the training phase. Inter-reader agreement will be assessed based on Fleiss's Kappa coefficient across the three radiologists and Cohen's Kappa between two radiologists, each associated with 95% confidence interval. The 20 patients will provide 83.32% power for testing agreement between two readers using the Kappa statistics to detect a true Kappa value of ≥ 0.75 against an unacceptable Kappa value of ≤ 0.3 , based on 1-sided normal test at a 0.1 level.

Intra-observer variability will also be assessed in the training phase. Each radiologist will read each patient's images twice (or even three times). After the first round of reading, the patients' images will be stored and the radiologists will be asked to review the same patients' images some time later, after the image orders have been perturbed and patient ID and previous evaluation results have been blinded. Integrating data from repeated evaluations from multiple radiologists on the 20 patients, generalize linear mixed effects model will be used to fit the reading results to characterize inter- and intra-reader variability based on an intra-class correlation coefficient (ICC). If a persistent large intra-reader variability is found (e.g., with $ICC > 0.3$), we will perform a focused interview with the radiologists to identify possible factors yielding inconsistency in reading results. Considering the influential factors, we will revise the training phase by providing more structured instructions illustrated with imaging examples to clarify potential issues. We expect improvement with structured instruction, but if intra-reader variability persists, we will consider requiring

repeated evaluations from the same radiologist on the same patient in order to robustly evaluate the diagnosis of US-guided DOT.

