We expect ~300 eligible women who will undergo SOC biopsy with valid US-DOT data and fall in the BIRAD categories of 3, 4A, 4B, 4C, or 5, rendering ~210 pathologically benign biopsies and 90 malignant biopsies. **For Study Hypothesis 1**, prior study results indicate the specificity was estimated to be no less than 45%. A total of 83 benign biopsies are needed to achieve 80.18% power to test Study Hypothesis 1 at a 2.5% level. This calculation is based on a 1-sided exact binomial test by conservatively assuming the true specificity is 45%, while 210 benign biopsies achieve 99.4% power to test Hypothesis 1. We also calculated the sample size based on the more stringent requirement that the lower limit of the 1-sided 97.5% conservative Clopper-Pearson binomial exact confidence interval (CI) (60) to the estimated specificity (of 45%) should exceed 30%. The 210 benign biopsies will allow us to estimate the 1-sided 97.5% exact CI to be between 37.7%~100%, thus satisfying this more stringent requirement. **For Study Hypothesis 2**, 90 malignant biopsies will achieve 89.33% power to conduct Study Hypothesis 2 at a 1-sided 2.5% level, based on a 1-sided exact binomial test. With 90 malignant biopsies, the sensitivity can be estimated at 98% with a 1-sided 97.5% exact CI of 92.06%~100%, thus satisfying the stringent criterion requiring a lower limit of >90%.

In calendar year 2016, over 7,000 women came to the Siteman Cancer Center at WashU for diagnostic evaluation. Approximately 17% had suspicious or highly suggestive malignancy findings and were recommended for tissue sampling. Over 700 women underwent US guided biopsy, which is more than 10 times larger than the potential study subjects each year.

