10.4 Data Analysis

All data will be analyzed as it is without imputations. Summary statistics will be used to summarize data including mean, median, standard deviation, interquartile range for continuous data and count (percentage) for categorical data.

All evaluable subjects will be analyzed. In addition to the specificity and sensitivity of US-guided DOT results, PPV, NPV, and overall accuracy will be calculated. The two study hypotheses will be tested by a binomial exact test and by constructing the one-sided 97.5% Clopper-Pearson exact confidence intervals for specificity and sensitivity. The lower limit will determine the achievement of study goals. We will explore the data further to refine the classification algorithm and the cut-off threshold. ROC analysis will evaluate the quantitatively measured tHb for pathological results of malignant biopsies. Besides tHb and its distribution, other parameters (such as oxyHb, deoxyHb, and distributions) will be either linearly incorporated with tHb to maximize the ultimate area under ROC or non-linearly through a tree-based classification model (e.g., using the R package “rpart”) (62).

The area under the ROC will be calculated to gauge the model's overall discriminative ability for biopsy results.

For the exploratory study (discordant biopsy results), the imaging data (e.g., tHb, oxyHb etc) will be summarized as appropriate in the subset of participants whose BIRAD results yield highly suspicious abnormalities (BI-RAD 4C, 5) but pathology yield benign results. Two sample t-test or Wilcoxon rank sum test as appropriate will be applied to compare this subset versus those with a malignant biopsy.

For the exploratory Study (CEM DOT correlation), we will compare BI-RADS assessments of CI&CEM vs. CI&US-guided DOT as well as correlate imaging data such as intensity of enhancement in CEM and the total hemoglobin level of US-DOT using Pearson or Spearman correlation coefficients. We will evaluate concordance/disconcordance between US-guided DOT and CEM using agreement measure (Kappa coefficient) and will test the discordance using McNemar test.

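### Section 10.4 fits the exploratory optical model and gauges it by AUC on the same patients with no internal validation, so that AUC will be optimistic

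*Combined protocol and SAP*

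**What the plan says.** Section 10.4 first sets out the two confirmatory tests, on specificity and sensitivity, with exact binomial limits, and closes them with "The lower limit will determine the achievement of study goals". It then turns to exploration: "We will explore the data further to refine the classification algorithm and the cut-off threshold". Optical parameters other than tHb "will be either linearly incorporated with tHb to maximize the ultimate area under ROC or non-linearly through a tree-based classification model", with the R package rpart as the example. The yardstick is then given: "The area under the ROC will be calculated to gauge" how well the model discriminates biopsy results.

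On the data used, the section says "All evaluable subjects will be analyzed" and names no other set. It does not say whether a tree would be pruned.

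Section 7.1 has the word validation in its title. It covers reader training on earlier cases, reader agreement and variability in about 20 patients, and Aims 1.1 to 1.4, but no validation of a fitted model. Of the training set it says "Data from the training study will not be used in the primary analysis". That set serves reader training and variability, and nothing makes it a test set for the model.

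**The concern.** A model tuned to a set of patients fits their noise as well as the signal. Its AUC in those patients is therefore higher, on average, than in new ones. In the linear arm of 10.4 the AUC is both the quantity maximised and the quantity reported. A cut-off re-selected on the same data has the same problem.

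The AUC is the only gauge of the fitted model that 10.4 names. If it is reported uncorrected, readers of the results cannot tell how much of the apparent gain from adding oxyHb, deoxyHb and distribution features to tHb is real. At stake is the credibility of the refined algorithm and cut-off that would go forward to later work.

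**Working it through.** **Inputs from the plan.** About 300 patients with valid data, "rendering ~210 pathologically benign biopsies and 90 malignant biopsies" (section 10.3). Candidate predictors are tHb, oxyHb, deoxyHb and their distributions, number not fixed (10.4). The model is a linear combination or a tree (10.4).

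**Assumptions, none of them in the plan.** Normally distributed markers, true tHb AUC 0.7 to 0.9, 3 to 12 predictors. The linear score is a logistic score, a proxy for direct maximisation of the AUC.

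**Step 1: the plan's own figures.** The plan gives no figure for the exploratory analysis, so only the sample-size base can be reproduced. For the exact one-sided test, take the smallest r with P(X ≥ r | n, p0) ≤ 0.025; power is P(X ≥ r | n, p1).
- n = 83, p0 = 0.30, p1 = 0.45: r = 34, size 0.0218, power 80.18% (stated 80.18%).
- n = 210, same rates: r = 77, size 0.0225, power 99.40% (stated 99.4%).
- n = 90, p0 = 0.90, p1 = 0.98: r = 87, size 0.0169, power 89.33% (stated 89.33%).

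**Step 2: definitions.** AUC = (R1 − n1(n1+1)/2) / (n1·n0), where R1 is the rank sum of the malignant cases, n1 = 90 and n0 = 210, so 90 × 210 = 18,900 pairs. Overstatement = AUC in the 300 patients used for fitting minus AUC of the same fitted model in a large independent sample. A tHb AUC of A corresponds to a mean shift d = √2·Φ⁻¹(A): 0.954 for A = 0.75 and 1.466 for A = 0.85.

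**Step 3: base simulation.** R rpart, 150 runs per setting, predictors correlated 0.3, extra predictors adding nothing beyond tHb.

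| tHb AUC | Predictors | Default tree: fitted → independent | Default tree: overstated | Pruned at minimum CV error | Pruned by 1-SE | Linear |
|---|---|---|---|---|---|---|
| 0.75 | 3 | 0.799 → 0.673 | 0.126 | 0.050 | 0.028 | 0.012 |
| 0.75 | 6 | 0.817 → 0.664 | 0.152 | 0.047 | 0.026 | 0.022 |
| 0.75 | 12 | 0.844 → 0.653 | 0.191 | 0.051 | 0.025 | 0.049 |
| 0.85 | 3 | 0.847 → 0.777 | 0.069 | 0.037 | 0.030 | 0.007 |
| 0.85 | 6 | 0.873 → 0.784 | 0.089 | 0.040 | 0.032 | 0.018 |
| 0.85 | 12 | 0.882 → 0.776 | 0.107 | 0.041 | 0.025 | 0.029 |

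(Overstatements were computed before rounding.)

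**Step 4: other assumptions.**
- tHb set equal to oxyHb plus deoxyHb; extra predictors uninformative or each with AUC 0.6; signal additive or with a threshold interaction. Default tree 0.04 to 0.21, 1-SE pruned 0.01 to 0.05, linear under 0.01 with 3 predictors and up to 0.036 with 10. The low end for the tree is 0.878 − 0.841 = 0.037 (3 predictors, tHb AUC 0.9); the high end is 0.824 − 0.610 = 0.214 (10 predictors, tHb AUC 0.7).
- A separate tree program with rpart's default settings and only tHb informative: default tree 0.05 to 0.23, linear about 0.01 to 0.045.

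**Step 5: refined cut-off.**
- Linear score, cut-off chosen for at least 98% apparent sensitivity: apparent 98.9%. Independent sensitivity was 96.7% to 97.9% at tHb AUC 0.75 and 0.85, so 1.0 to 2.2 points too high. With no signal at all and 12 predictors it was 95.3%, or 3.6 points too high. Specificity moved by 1 point or less.
- Linear score, Youden cut-off: index 0.582 apparent against 0.527 independent (3 predictors, tHb AUC 0.85), a gap of 0.055. With 12 predictors and tHb AUC 0.75 it was 0.451 against 0.322, a gap of 0.129.
- tHb alone, Youden cut-off: sensitivity 3 to 4 points too high, specificity about 1 point.

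**Step 6: what is not biased.** For raw tHb with nothing fitted, the mean simulated AUC was 0.751 and 0.851 against true values of 0.75 and 0.85.

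**Step 7: does a correction work?** In the Step 4 settings with tHb = oxyHb + deoxyHb, 10-fold cross-validated AUC minus truth was −0.022 to +0.003 for the default tree and −0.022 to +0.008 for the linear score. With an additive signal, bootstrap optimism correction was within 0.01 for the linear score but left up to 0.08 for the unpruned tree. Example (10 predictors, tHb AUC 0.7, tree): apparent 0.824, bootstrap 0.690, cross-validated 0.599, truth 0.610.

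**The case against.** The best defence is that 10.4 presents this work as exploration and has already tied success to the confidence limits. That stands, and it confines the point to exploratory results. It does not remove the point: the section specifies the methods, an example package and the metric, and leaves out only the step that makes the metric interpretable.

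Second, rpart is only an example and pruning may be intended. With pruning the overstatement is small, and for a linear score with three predictors it is about 0.01. This stands too; the large figures belong to an unpruned tree. rpart does run cross-validation for its complexity table, but that neither prunes the tree nor corrects the AUC.

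Three stronger readings are tempting, and the documents do not support them:
- A reader might infer very large losses at the refined cut-off from the default tree's own classes (for example 65.5% apparent sensitivity against 48.2% in independent data, with 6 predictors and tHb AUC 0.8). Section 2 wants a cautious threshold under which cancers are rare, and a rule with that sensitivity is not such a threshold. Section 10.4 also does not say that sensitivity or specificity at a refined cut-off will be reported.
- A reader might infer that the uncorrected AUC will pick the wrong model type. The plan does not say that the AUC will choose between linear and tree.
- A reader might infer misleading confidence intervals for the AUC. The plan names none.

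**Conclusion.** The point holds for the exploratory part of 10.4. Followed as written, the AUC of the fitted model comes from the patients used to fit it and is too high. At 90 malignant and 210 benign, the overstatement is about 0.04 to 0.23 for a default unpruned tree, about 0.01 to 0.05 for a pruned tree, and about 0.01 (3 predictors) to 0.05 (10 to 12 predictors) for a linear score. If a refined cut-off is reported, one set for at least 98% apparent sensitivity overstates sensitivity by about 1 to 4 points, the upper end only where the markers carry no signal, and specificity by about 1 point or less. A Youden cut-off on a linear score of several predictors overstates the index by about 0.06 to 0.13. These sizes depend on the assumed marker distribution, signal strength and number of predictors. The larger bias for the unpruned tree than for the other two models appeared at every setting in the Step 3 table.

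A reader might also infer that the trial's main result, the share of benign biopsies that could be avoided, is inflated. It is not. Section 7 defines the test result from readers' assessments: "Combined CI and US-guided DOT BI-RADS 2 and 3 assessments will be considered test negative". The confirmatory tests use those calls, not the fitted model or its cut-off. The change is worth making, but the confirmatory conclusions do not depend on it.

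**What to change.** State in 10.4 that:
- the AUC of any fitted model, and any sensitivity or specificity reported at a refined cut-off, will be cross-validated by patient (for example 10-fold), repeating variable choice, weights, tree growing and pruning, and cut-off choice within each fold;
- bootstrap optimism correction is an acceptable alternative for the linear score, but cross-validation is preferred for a tree;
- the tree will be pruned by a named rule;
- any comparison of linear and tree models will use the corrected AUC;
- the refined algorithm and cut-off are exploratory until validated in independent patients.

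The cost is a few lines of text and a little more code, with no extra patients or data. The reported exploratory AUC will be lower, mostly for an unpruned tree, and cross-validation is itself slightly pessimistic, by about 0.02.

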2 OBJECTIVES

We have received 5-year NCI funding to support this study.

The primary objective of this study is to assess the ability of US-guided DOT to reduce the rate of benign biopsy. To achieve this objective we will simultaneously acquire co-registered US imaging data and US-guided DOT imaging data from a group of patients (~300) scheduled for US-guided breast biopsy. We hypothesize that the additional optical information of tHb concentration and distribution will lead to a downgrading of the assessment of a subset of low to moderate suspicion

abnormalities based on conventional imaging (i.e. breast ultrasound with or without mammography) and thereby could lead to a reduction in benign breast biopsies (i.e. false positives).

The secondary and complementary objective is to assess the impact on sensitivity of adjunctive optical data. In particular we hypothesize that by defining a conservative tHb threshold below which malignancy is so rare that the addition of US-guided DOT will not significantly alter the sensitivity of the combined US-guided DOT & CI assessment, i.e. adjunctive US-guided DOT will not decrease true positives.

A third objective is to assess the impact of adjunctive US-guided DOT data in the management of discordant pathology results. In current SOC, the radiologist performing the needle biopsy routinely compares the imaging with the pathology results for concordance. Highly suspicious abnormalities (BI-RAD 4C, 5) that yield benign results are typically considered discordant and are recommended for repeat biopsy or surgical excision. If the discordant abnormality has a tHb below the minimum threshold value, this might allow radiologists to forego a repeat biopsy or surgery. For example, focal fibrosis may appear highly suspicious on US. Our initial data show that fibrotic lesions have low vascularity (28).

Additionally as an exploratory objective, we will compare the results of US-guided DOT and in particular tHb concentration with contrast enhanced mammography (CEM) in the subset of patients who undergo CEM.

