From a total of 300 patients who undergo the US-DOT exam, we expect to recruit a small subset of patients with BI-RADS 4C or 5 lesions whose biopsy results are benign. We will correlate initial biopsy results, optical data and gold standard final pathology for this subset of patients. This pilot data will allow us to assess the potential benefit of US-guided DOT in managing discordant abnormalities, i.e. reducing additional invasive procedures of a subset of benign abnormalities.

Exploratory Aim 1.4 Explore and compare US-guided DOT and CEM
In this exploratory aim, we will evaluate the agreement (Kappa coefficient) of US-guided DOT and CEM, as both modalities measure alterations in lesion vascularity. We will compare BI-RADS assessments of CI&CEM vs. CI&US-guided DOT as well as correlate imaging data such as intensity of enhancement in CEM and the total hemoglobin level of US-DOT.

Alternative plan: *If US-guided DOT is not comparable with CEM we will evaluate the capability of US-guided DOT in improving the accuracy of combined CI&CEM because CEM may become SOC in a significant subset of patients.*

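### Section 10.4 does not carry through the Aim 1.3 plan to relate optical data to final pathology within discordant lesions, and the one test it names cannot answer the aim

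*Combined protocol and SAP*

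**What the plan says.** Section 2 gives the third objective as a threshold decision within one group, namely highly suspicious lesions whose biopsy came back benign: "If the discordant abnormality has a tHb below the minimum threshold value, this might allow radiologists to forego a repeat biopsy or surgery".

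Under Aim 1.3, section 7.1 plans an analysis inside that group: "We will correlate initial biopsy results, optical data and gold standard final pathology for this subset of patients". It names no statistic, threshold or interval. It gives the size of the group only as small ("we expect to recruit a small subset of patients with BI-RADS 4C or 5 lesions whose biopsy results are benign") and treats the result as pilot data: "This pilot data will allow us to assess the potential benefit of US-guided DOT in managing discordant abnormalities".

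Section 10.4 labels this analysis exploratory. It defines the subset as participants "whose BIRAD results yield highly suspicious abnormalities (BI-RAD 4C, 5) but pathology yield benign results", without saying whether initial or final pathology is meant. For that subset "the imaging data (e.g., tHb, oxyHb etc) will be summarized as appropriate". One test follows: "Two sample t-test or Wilcoxon rank sum test as appropriate will be applied to compare this subset versus those with a malignant biopsy". The malignant group is not restricted to BI-RADS 4C or 5.

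**The concern.** A reader using tHb to decide about a discordant lesion needs to know what share of such lesions fall below the threshold, which is the possible saving in procedures. The reader also needs the share of those that prove malignant, which is the price. A comparison of imaging values, by mean or by rank, between discordant lesions and lesions already shown to be cancer yields neither figure. For the second group, forgoing further sampling is not in question, because the biopsy has already given the answer.

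The undefined word for pathology in section 10.4 adds to this. If it means the initial biopsy, cancers found later are counted in the benign group. If it means final pathology, those cancers leave the subset, and the risk of missing them cannot be seen.

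At stake is interpretation. A small p-value could be taken as support for fewer repeat procedures when it carries no information on how many cancers would be missed.

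**Working it through.** **No figure of the plan's own to reproduce.** The documents give no subset size, effect size, significance level or power for Aim 1.3. The powers in section 10.3 belong to the specificity and sensitivity hypotheses.

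**What the aim needs against what section 10.4 gives**

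| Needed for the aim | Section 10.4 |
|---|---|
| Subset defined by a benign initial biopsy | Benign pathology, initial or final not stated |
| Share of the subset below the tHb threshold | Not specified |
| Share of those below it that are malignant on final pathology | Not specified |
| A threshold fixed in advance | None fixed for this aim; further exploration is planned to refine the cut-off |
| A rule for lesions not sampled again | None |

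Section 10.4 also lists predictive values, overall accuracy and a receiver operating characteristic analysis of tHb. None is specified for the discordant subset.

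**Can the named test tell useful tHb from useless tHb within the subset?** A simulation with 2,000 trials per setting used a two-sample t-test at two-sided 0.05.

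- From the documents: about 90 malignant biopsies (section 10.3).
- Assumed: normally distributed tHb with SD 35, mean 50 in truly benign discordant lesions and 90 in the malignant comparator; 10 to 30 discordant lesions, of which 1 to 5 are cancers missed at first biopsy. The subset is defined by the initial biopsy, so these cancers sit in it.
- Case A: missed cancers have mean 50, so tHb has no discrimination within the subset (area under the curve about 0.50).
- Case B: missed cancers have mean 90, so tHb discriminates (area about 0.79).

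| Discordant lesions (missed cancers) | t-test significant, case A | t-test significant, case B | Rank-sum within subset significant, case B |
|---|---|---|---|
| 10 (1) | 93.8% | 85.8% | 0% |
| 15 (2) | 98.0% | 93.8% | 22.0% |
| 20 (3) | 99.6% | 96.5% | 33.4% |
| 30 (5) | 100% | 99.1% | 57.8% |

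The planned comparison is significant nearly always in both cases, and slightly more often in case A, where tHb is of no use for the decision. The last column shows that a significance test inside the subset would usually fail too. With 1 cancer in 10 lesions, the smallest possible two-sided exact p-value is 2/10 = 0.20. Estimation with intervals therefore suits this aim better than testing.

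**Precision of the estimate that is needed.** With 0 cancers among m lesions below the threshold, the exact one-sided 97.5% upper limit is 1 − 0.025^(1/m), for assumed m:

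- m = 5: 1 − 0.025^(1/5) = 0.522
- m = 10: 1 − 0.025^(1/10) = 0.308
- m = 15: 1 − 0.025^(1/15) = 0.218
- m = 20: 1 − 0.025^(1/20) = 0.168
- m = 30: 1 − 0.025^(1/30) = 0.116

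**The case against.** The best defence is that section 7.1 already plans the right analysis: optical data against final pathology within the discordant subset. A reader of section 10.4 alone might infer that the comparison with malignant biopsies is the whole of Aim 1.3. The documents do not support that. What stands is narrower: the intention in section 7.1 is never turned into a statistic, and the only test named is a different one.

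A reader might also infer that the benign group is contaminated by missed cancers. That follows only if pathology in section 10.4 means the initial biopsy, and the text does not say so. Nor is the comparison one of mean tHb alone, since a rank test is allowed and other imaging parameters are included. That the comparator takes in cancers from all BI-RADS categories is the natural reading, but the text does not state it.

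The aim is exploratory, the data are called pilot data, and no success criterion depends on the p-value. As a first look the contrast has some value: if discordant benign lesions had tHb like that of cancers, the proposed use would be implausible. This limits the weight of the point. It does not make the test answer the question.

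**Conclusion.** The point holds as a gap between two sections and a mismatch between aim and test. Section 10.4 does not carry through the analysis within the subset that section 7.1 promises, and its named test cannot give the share of discordant lesions below the threshold or the share of those that are cancers. This does not depend on the simulation.

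The size does depend on assumptions. The 94% to 100% and 86% to 99% rest on assumed means, SD, subset sizes and numbers of missed cancers. The 31% upper limit for 0 of 10 shows how little a small subset can establish under an assumed count. It is not a measure of harm from the t-test, and the same uncertainty would remain under the fix, though it would then be reported.

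The change is a worthwhile improvement at low cost. It does not bear on the specificity or sensitivity hypotheses.

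**What to change.** In section 10.4:

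- Define the subset as BI-RADS 4C or 5 lesions with a benign initial biopsy.
- Tabulate tHb below or above the protocol's minimum threshold against final pathology. State the threshold and fix it before this analysis. Section 1.1 cites a value of 50 from earlier work on 4A and 4B lesions, and section 2 refers to a minimum threshold without a number. The cut-off refined on the same data should not be used.
- Report the proportion of the subset below the threshold and, among those with final pathology, the proportion malignant, each with an exact confidence interval.
- Report separately the lesions that had no further sampling, whose final pathology is unavailable.
- Keep any comparison with malignant biopsies as descriptive only, restricted to 4C and 5 lesions and classified by final pathology.

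The cost is SAP wording, using data that section 7.1 already plans to use. There are two limits. The intervals will be wide, because the subset is small. Final pathology will be incomplete, because section 7 collects surgical pathology only where it exists.
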